### 4) Outcome measures

In consultation with the Diabetes Subcommittee of the NYC-CDRN, the following outcome measures have been identified (see table below). As with the identified process measures, these are metrics identified and developed by major quality reporting organizations, which means that results will be readily interpretable by policymakers and easily compared to other studies and datasets.(30)

In order to assess these metrics, and to perform individual-level longitudinal analyses, we will evaluate health system utilization and intermediate and long term outcomes. Outcomes will include:

- 1) Intermediate outcomes:HbA1c, blood pressure, LDL and renal function
- 2) Long-term outcomes: we will use validated ICD-9 code based-algorithms to assess
  - a. macrovascular outcomes (stroke and myocardial infarction)
  - b. microvascular outcomes (nephropathy, end-stage renal disease, neuropathy, amputation, retinopathy, and blindness)
- 3) Utilization outcomes:
  - a. Number and diagnoses associated with diabetes-related preventable hospitalizations
    - i. uncontrolled diabetes admissions
    - ii. diabetes short-term complications admissions (diabetic ketoacidosis, hyperosmolarity, coma)
    - iii. and long-term complications admissions (renal, eye, neurological, and circulatory disorders)
  - b. ER visits
  - c. Outpatient visits.

Table 3. Outcome measures	
Metric	
HbA1c Control (<8.0%) (NCQA)	
HbA1c Poor Control (>9.0%) (NCQA)	
Blood Pressure Control (<140/90 mm Hg) (NCQA)	
Uncontrolled Diabetes Admissions Rate (PQI 14) (AHRQ)	
Diabetes Short-Term Complications Admissions (PQI 1) (AHRQ)	
Diabetes Long-Term Complications Admissions (PQI 3) (AHRQ)	
Lower-Extremity Amputation Among Patients With Diabetes (PQI 16) (AHRQ)	
Medical Attention for Nephropathy (NCQA)	

**Activity 2:** For this qualitative research, we will identify cross-cutting themes from interviews.

**Activity 3:** Data collected through these interviews will be utilized to categorize HH, CMA, and care manager activities and experiences.

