Our sample will include Medicaid enrollees with diabetes who are seen at NYC-CDRN sites and in HHs (estimated 6,500-20,000) and a matched comparison group of Medicaid enrollees with diabetes who are part of the NYC-CDRN, but not HHs. We plan to develop a set of propensity score matched controls, based on a set of patient, practice, and market-level (zip-code) characteristics. We will use quasi-experimental methods to investigate the magnitude of the effects of the HHs program between 2010 and 2017. This secondary data analysis is referred to as **Activity 1** in this protocol. In addition, we will gather information regarding the patient experience of HHs through interviews (**Activity 2**). We will also utilize interviews with HH leaders and care managers from NYC HHs to further characterize these entities (**Activity 3**). Columbia University will participate in only **Activity 1**.

8/20/20 update: Apart from evaluating the impact of the NYS Medicaid HH program on the process and outcomes of care for low-income NYC residents with diabetes, compared to non-enrolled residents with similar conditions and utilization histories, we have received funding to extend this work to examine the impacts of the COVID-19 pandemic on this vulnerable population, a majority of which is Black or Latinx. We hypothesize that HH participation will reduce pandemic-related disruptions in access to health care and social services and improve health outcomes among patients with diabetes in NYC. Using a quasi-experimental difference-in-differences design, we will contrast access and utilization of health care and social services and health outcomes among HH enrollees and non-enrollees during a baseline period prior to the pandemic (CY2019) with each month of the pandemic time period (2020).

**Aim 4:** Using Medicaid claims data, we will estimate the impact of HH enrollment compared to usual care among Medicaid-insured patients with diabetes and other chronic conditions on access to health care and social services and COVID-19 and non-COVID-19 clinical outcomes, as well as racial/ethnic disparities in these outcomes, before and during the pandemic in NYC.

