### **Affordable Care Act and Medicaid Health Homes**

As part of the Patient Protection and Affordable Care Act (ACA) of 2010, “health homes” were authorized for care management and coordination for individuals enrolled in Medicaid. Under the ACA, six health home services are eligible for reimbursement: comprehensive care management, care coordination and health promotion, comprehensive transitional care, patient and family support, referral to community and social support services, and use of health information technology to link services.(16) As such, the Medicaid Health Home (HH) includes interventions previously tested among individuals with diabetes. However, the payment reforms associated with these new care delivery mechanisms add another aspect to the intervention. In addition, these types of interventions are now being expanded to include a larger patient population- those eligible for HHs. In order to be included in a HH, patients need to have chronic conditions, including serious mental illness, substance use disorders, or multiple chronic diseases, including diabetes. As of November 2014, 20 states had approved plans for HHs.(17)

New York State (NYS) established a Medicaid Health Home program in 2012, with the New York State Health Home State Plan Amendment (SPA). In New York State at the end of 2014, over 5 million low-income individuals were enrolled in Medicaid, including over 3 million of NYC’s estimated 8.4 million residents.(18, 19) The State estimated in 2012 that approximately 1 million individuals would be eligible for the HH program, including 418,677 Medicaid recipients with mental health or substance use disorders, and 386,399 participants with other chronic conditions. HHs were rolled out in three phases during 2012, with Phase I in January (which included the Bronx and Kings (Brooklyn) Counties), Phase II in April (which included New York (Manhattan), Queens and Richmond (Staten Island), the remaining counties in NYC), and Phase III in July.(20) As of August 2014, 40,776 individuals were enrolled in NYC.(21, 22) Around 35,000 Medicaid enrollees across NYS were part of precursor care management programs (including the Office of Mental Health’s Targeted Case Management Program (for those with severe mental illness), Managed Addiction Treatment Services Program, and the Comprehensive Medicaid Case Management Program (for people living with HIV/AIDS), which are all in the process of converting to HHs.(16)

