The identification of individuals eligible for HHs is initiated by one of two processes: a NYS Department of Health (DOH) predictive algorithm utilizing Medicaid services data, which prioritizes individuals based on risk of future hospitalization; and community or “bottom up” referrals from healthcare providers, community-based care management providers, including harm reduction providers, and other agencies such as those who serve individuals re-entering the community from jail or prison. Enrollment in HHs has been slower than expected, and several challenges have been identified and are being addressed by the NYS DOH. These include inaccuracies in the lists of targeted individuals, challenges in the recruitment process, and individuals electing not to participate in the program.(16) The new program may put stress on already under-resourced facilities, by increasing the complexity of billing, the requirements around health information technology (HIT), the caseloads of facilities and case managers, and, in some cases, lowering reimbursement for care management services. Another significant change brought about by HHs is the expanded scope of health conditions of clients served by care management agencies that formerly provided case management for people living with HIV/AIDS, substance use disorders, or serious mental illness ([name], personal communication, March 9, 2015).

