**b) Inclusion and Exclusion Criteria**

**Activity 1:** For this analysis, the study cohort will consist of patients who: 1) have Type II diabetes, 2) are insured by Medicaid, and 3) are either part of a Health Home or meet criteria for Health Home enrollment, but are not enrolled in a Health Home.

1) In consultation with the Diabetes Subcommittee of the NYC-CDRN, this protocol will use the SUPREME-DM definition of diabetes, which has been previously validated.(29) This definition has been adopted as a standard across the three CDRNs that have diabetes as a disease focus (New York, Louisiana, and Oregon-Advance). It consists of the following algorithm (see Table 1), where any of the listed criteria are sufficient for inclusion for any patient with at least one outpatient visit at a participating CDRN site within the past year.

Table 1. Diabetes Definition	
Criteria	Parameter
ICD9/10 - Inpatient discharge diagnosis	1 or more of (250.x, 357.2, 366.41, 362.01–362.07)
ICD9/10 - Outpatient diagnosis	2 or more of (250.x, 357.2, 366.41, 362.01–362.07) Visits must occur on separate days. Ambulatory visits only.

HbA1c	2 or more HbA1c's at >=6.5%	Tests must be on separate days no more than 2 years apart.
Fasting Plasma Glucose	2 or more at >= 126 mg/dL	Tests must be on separate days no more than 2 years apart.
Random Plasma Glucose	2 or more at >= 200 mg/dL	Tests must be on separate days no more than 2 years apart.
Random plasma plus fasting glucose	1 at >= 200 mg/dL AND 1 at >= 126 mg/dL	Tests must be on separate days no more than 2 years apart.
HbA1c plus fasting glucose	1 at >= 6.5% and 1 at >= 126 mg/dL	Tests can occur on same day but cannot be more than 2 years apart.
HbA1c plus random plasma glucose	1 at >= 6.5% and 1 at >= 200 mg/dL	Tests can occur on same day but cannot be more than 2 years apart.
2-h 75-g OGTT	1 at >= 200 mg/dL	Do NOT count if measured during pregnancy.
Medications	Sulfonylurea, insulin, biguanide, SGLT-2 inhibitors, thiazolidinedione, alpha-glucosidase inhibitor, incretin mimetic, meglitinide, amylin analog, or dipeptidyl peptidase inhibitor	>= 1 prescription. If dispense was for metformin, any thiazolidinedione, or exenatide, at least one lab test (HbA1c > 6.5%, random glucose >= 200 mg/dL, fasting glucose >= 126 mg/dL) is also required.

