**d) Study Timelines**

**Activity 1:** This is a retrospective cohort analysis. We will examine two data sets: one with data from 2007-2014, and one with data from 2010-2017. The project has been funded from 3/1/2016-2/28/2021.

**Activity 2:** We completed our year 2 focus groups and interviews by 8/31/2018 and we anticipate completing year 5 focus groups by 2/2021. Participation in the study will consist of being a part of an interview, and optional follow up activities (receiving study results). The project has been funded from 3/1/2016-2/28/2021.

**Activity 3:** We completed our first round of HH leadership interviews by 8/31/18. Year 5 interviews will be conducted by 2/2021. The project has been funded from 3/1/2016-2/28/2021.

**Activity 4:** We anticipated conducting primary analyses by 6/30/2021.

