**e) Variable and endpoints**

**Activity 1 and 4:** For this aspect of the study, we will examine multiple endpoints related to process of care, outcomes, and racial/ethnic disparities. We will examine variable and endpoints in the following categories:

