**2) Health home indicators and patient co-morbidities**

Indicators available include whether the individual was enrolled in the HH program, the date of joining the program, the name/location of the HH, patient-level co-morbidities and chronic conditions (additional diagnoses).

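### Eight long-term outcomes are tied to ICD-9 algorithms, although the data run to 2017 and beyond and the protocol elsewhere expects ICD-10 records

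*Protocol*

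**What the plan says.** Section 5(e), item 4) Outcome measures, sets the rule for long-term outcomes: "we will use validated ICD-9 code based-algorithms to assess" two macrovascular outcomes (stroke and myocardial infarction) and six microvascular ones (nephropathy and end-stage renal disease, retinopathy and blindness, neuropathy, amputation). ICD-10 is not mentioned there, and no other section extends these algorithms to it.

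The opening of Section 5(e) is headed for Activities 1 and 4 together and says "we will examine multiple endpoints related to process of care, outcomes, and racial/ethnic disparities".

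The data years are given elsewhere. For Activity 1, Section 1) Objectives plans to "investigate the magnitude of the effects of the HHs program between 2010 and 2017", and Section 5(d) Study Timelines says "We will examine two data sets: one with data from 2007-2014, and one with data from 2010-2017". For Activity 4, Section 1 compares calendar year 2019 with each month of 2020 in Medicaid claims.

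The cohort definition in Section 5(b), Table 1, labels its rows for both code systems, for example "ICD9/10 - Inpatient discharge diagnosis".

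**The concern.** The protocol expects ICD-10 records when it selects patients but names only ICD-9 when it counts their long-term events. An analyst who follows the outcome sentence literally would find no stroke, infarction or microvascular event in any record coded in ICD-10. The patients and their follow-up time would remain in the data set, but their events would not be selected.

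These eight outcomes are the named long-term part of Aim 2, and Aim 3 examines disparities in outcomes as well. The unread months come at the end of the 2010-2017 set, after the program started, which is when any effect has to appear. Exposure starts at "the date of joining the program", so the unread months take a larger share of follow-up from people who joined late. Late joining is to be expected, since Section 2 reports that "Enrollment in HHs has been slower than expected".

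**Working it through.** The protocol gives no event count, power or precision figure on this point, so there is no stated number to reproduce. The check compares the text across sections and then counts calendar months.

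**Text comparison**

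| Item | Where | What it fixes |
|---|---|---|
| Long-term outcomes | 5(e), item 4 | ICD-9 algorithms; 2 + 6 = 8 outcomes |
| Reach of the endpoint section | 5(e), opening | Activities 1 and 4 |
| Activity 1 data | 1 and 5(d) | 2007-2014 and 2010-2017 |
| Activity 4 data | 1 | 2019 and 2020 claims |
| Cohort diagnosis rows | 5(b), Table 1 | Labelled for ICD-9 and ICD-10 |
| Program roll-out | 2 | From January 2012 |

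The inconsistency follows from this table alone. The changeover date affects only its size.

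**Assumption.** The date on which records move from ICD-9 to ICD-10 is not in the document. I take October 2015 and vary it by 12 months either way.

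**Formula.** Share uncaptured = months from changeover to end of window / months in window.

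Months from changeover to December 2017:
- October 2015: 3 + 12 + 12 = 27
- October 2016: 3 + 12 = 15
- October 2014: 3 + 12 + 12 + 12 = 39

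| Window | Months | Changeover Oct 2015 | Oct 2016 | Oct 2014 |
|---|---|---|---|---|
| 2010-2017 set | 96 | 27/96 = 28% | 15/96 = 16% | 39/96 = 41% |
| Joined January 2012, followed to end 2017 | 72 | 27/72 = 38% | 15/72 = 21% | 39/72 = 54% |
| Joined August 2014, followed to end 2017 | 41 | 27/41 = 66% | 15/41 = 37% | 39/41 = 95% |
| 2007-2014 set | 96 | 0/96 = 0% | 0/96 = 0% | 3/96 = 3% |

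The two joining dates are illustrations. January 2012 is the start of roll-out. August 2014 is the date of the enrolment count in Section 2 ("As of August 2014, 40,776 individuals were enrolled in NYC"), not a typical joining date; the distribution of joining dates is not in the document. Both rows assume unbroken follow-up to December 2017.

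**Activity 4.** All 24 months of 2019-2020 lie after every assumed changeover date. If those claims are coded in ICD-10 and these outcomes are used there, no event would register before or during the pandemic. Aim 4 speaks only of clinical outcomes in general, so I put no percentage on this.

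**What is covered elsewhere.** Table 3 and the utilization list are not bound by the ICD-9 sentence. They give partial cover through the amputation indicator (PQI 16), the nephropathy-attention metric, renal function, and admissions for long-term renal, eye, neurological and circulatory complications. Stroke and myocardial infarction are named as endpoints only under the ICD-9 sentence.

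**The case against.** The strongest reply is that the phrase is shorthand. The sentence does not say that only ICD-9 will be used. Table 1 itself carries a single code list under its dual label, so the authors may have meant both systems throughout and left the code versions to a code book. The single list in Table 1 is real and is a related gap. But Table 1 at least names ICD-10, and the outcome sentence does not. If both systems are intended, the sentence is wrong and should say so.

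A second reply is that enrollees and comparison patients lose the same calendar months, so the contrast is protected. That holds in part. If the uncaptured share of follow-up is the same in both groups, a ratio of rates may be little affected. A difference in rates is not protected if the unread months are kept as event-free time. With equal baseline rates, a constant additive effect and follow-up over all of 2012-2017, the estimate would shrink to 1 - 27/72 = 0.63 of its true size (0.46 to 0.79 over the assumed range). Those conditions are illustrative, so I do not claim this as the bias. Even with a shared loss, events and precision are lost.

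Three further points stand as limits. Months are not events, and lasting conditions may first be recorded before the changeover. Section 5(b) requires Medicaid coverage only at some point in 2010-2016, so actual follow-up may be shorter than the illustrations. And mapping codes from a validated ICD-9 algorithm does not make the ICD-10 version validated.

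**Conclusion.** The concern holds. The protocol states a rule for eight outcomes that does not fit its own data years or its own expectation of ICD-10 records. This is a wrong statement, not a detail left to the analysis plan: an analysis plan that used ICD-10 would contradict it.

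For the 2010-2017 set, about 28% of calendar months go uncaptured (16-41%), all after roll-out began, with a larger share for later joiners. This rests on the assumed changeover of October 2015, plus or minus 12 months. The 2007-2014 set is essentially unaffected. The consequence I would state firmly is missed events and lost precision for the long-term outcomes, most clearly for stroke and myocardial infarction. Bias between groups is possible if baseline rates, event timing or follow-up differ, but its size is not established. The effect on Activity 4 is conditional on ICD-10 coding and on these outcomes being used. The point should be fixed before the 2010-2017 long-term analysis is relied on.

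**What to change.** In Section 5(e), item 4, change the long-term outcome sentence so that it names validated algorithms for both ICD-9 and ICD-10, applied by date of service. Identify the algorithm used for each of the eight outcomes, and where no validated ICD-10 version is found, say so. State whether these outcomes are used in Activity 4. Tabulate long-term event counts by group across the changeover in the 2010-2017 set, to show any break in ascertainment. When making the edit, reconcile the dual label in Table 1 with its single code list.

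The cost is one phrase, a code list per outcome and one table. Section 5(f) says the limited data sets hold actual dates, so the date rule can be applied to data already held.

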Similar care management programs have been shown, in studies of limited scope, to improve intermediate outcomes for patients with diabetes. However, the impact of HHs on processes of care and outcomes among low-income patients with diabetes mellitus in large, diverse, and complex urban settings remains largely unexplored. Additionally, current research on the impact of HHs, both in NYS and elsewhere, does not incorporate individual-level clinical data on chronic disease management. As a result, whether the Medicaid HHs program has impacted the health of patients with diabetes has not been examined. It is also not known how interventions of this scope will affect long-standing racial and ethnic disparities in the quality of care and outcomes of individuals with diabetes. Since similar programs are being implemented nationally, it now is critically important to evaluate the effects of HHs on the process and outcomes among patients with diabetes, a condition with multiple complications, which are disproportionately prevalent among racial and ethnic minorities and low-income populations in the United States.

We plan to use two complementary sources of longitudinal individual-level data: 1) NYS Medicaid administrative and claims data and 2) the New York City-Clinical Data Research Network (NYC-CDRN), funded by the Patient-Centered Outcomes Research Institute (PCORI). The NYC-CDRN has identified a cohort of patients with diabetes (approximately 90,700 Medicaid enrollees with diabetes) from 7 large health systems based on electronic health record data; and it has developed a common data model that includes clinical variables related to the process and outcomes of care of patients with diabetes. Using information available from the two complementary data sources and quasi-experimental methods, we will assess the impact of Medicaid HHs in NYC.

Among adult Medicaid patients with diabetes in NYC, we propose:

**Aim 1:** To assess the impact of HHs on the process of care for patients with diabetes.

**Aim 2:** To assess the impact of HHs on the health outcomes of patients with diabetes.

**Aim 3:** To assess the impact of HHs on racial and ethnic disparities in the process of care and outcomes among Medicaid patients with diabetes.

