### 3) Process measures

In consultation with the Diabetes Subcommittee of the NYC-CDRN, the following process measures have been identified (see Table 2). Several organizations in the United States have developed sets of quality metrics that can be used to evaluate the adequacy and appropriateness of processes of care and outcomes for patients with diabetes. These include the Centers for Medicare and Medicaid Services (CMS), the Pharmacy Quality Alliance (PQA), the National Committee for Quality Assurance (NCQA)'s Healthcare Effectiveness Data and Information Set (HEDIS), and the Agency for Healthcare Research and Quality's (AHRQ) Prevention Quality Indicators (PQI) (which assess the quality of care for "ambulatory care sensitive conditions," also known as preventable admissions).(30-33)

Table 2. Process Measures	
Metric	Component
Adherence to Chronic Medications (CMS)	At least two prescriptions for statins and a Proportion of Days Covered (PDC) of at least 0.8 during the measurement period (12 consecutive months)
Adherence to Chronic Medications (CMS)	At least two prescriptions for ACEIs/ARBs and a PDC of at least 0.8 during the measurement period (12 consecutive months).
Adherence to Chronic Medications (CMS)	At least two prescriptions for a single oral hypoglycemic agent or at least two prescriptions for multiple agents within an antidiabetic class and a PDC of at least 0.8 for at least 1 antidiabetic class during the measurement period (12 consecutive months).
Eye Exam (NCQA)	Received a retinal or dilated eye exam during the measurement year or a negative retinal or dilated eye exam in the year prior to the measurement year.
HbA1c testing (NCQA)	Received an HbA1c test during the measurement year.
LDL-C Screening (NCQA)	Received an LDL-C test during the measurement year.
Medical Attention for Nephropathy (NCQA)	Received a nephropathy screening test or had evidence of nephropathy during the measurement year.
Appropriate Treatment of Hypertension (PQA)	If dispensed a medication for diabetes and hypertension, are receiving an angiotensin-converting -enzyme-inhibitor (ACEI) or angiotensin receptor blocker (ARB) or direct renin inhibitor (DRI) renin-angiotensin-antagonist medication.
Foot exam (NCQA)	Received a foot exam (visual inspection with either a sensory exam or a pulse exam) during the measurement year.

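### Nephropathy, neuropathy and retinopathy are counted as adverse outcomes by diagnosis code, while the examinations that find them are process measures that Health Homes are expected to increase

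*Protocol*

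**What the plan says.** Section 1, Objectives, sets two aims for the same population. Aim 1 is "To assess the impact of HHs on the process of care for patients with diabetes" and Aim 2 is "To assess the impact of HHs on the health outcomes of patients with diabetes".

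Section 5e, Process measures, Table 2, includes three examinations among its nine measures:

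- eye exam: "Received a retinal or dilated eye exam during the measurement year or a negative retinal or dilated eye exam in the year prior";
- medical attention for nephropathy: "Received a nephropathy screening test or had evidence of nephropathy during the measurement year";
- foot exam: "Received a foot exam (visual inspection with either a sensory exam or a pulse exam) during the measurement year".

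Section 5e, Outcome measures, introduces the second outcome category with "Long-term outcomes: we will use validated ICD-9 code based-algorithms to assess" and lists under it "microvascular outcomes (nephropathy, end-stage renal disease, neuropathy, amputation, retinopathy, and blindness". Table 3 in the same section has lower-extremity amputation as a metric of its own. It also repeats the nephropathy-attention metric from Table 2.

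Section 2, Medicaid Health Homes and Diabetes Management, expects HHs ideally to improve both process and outcomes, and names specialist evaluation as one of the routes.

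**The concern.** A code-based diagnosis is counted only after someone has looked for the condition and recorded it. For retinopathy, nephropathy and neuropathy, the looking is largely done by examinations that Table 2 scores as good care. A programme that increases those examinations therefore also increases the chance that existing disease is coded. At equal true disease, the HH group would show more of these three outcomes. If HHs truly reduce early disease, the extra detection would offset part or all of the reduction.

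Nephropathy shows the conflict most plainly. Evidence of nephropathy meets the process measure, yet nephropathy is also an adverse long-term outcome, so the same coded diagnosis is scored in opposite directions.

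Section 1 plans propensity-score matching on patient, practice and zip-code characteristics. That balances the groups at the start. It cannot balance screening that happens after enrolment because of the programme. At stake is the reading of Aim 2 for these outcomes: a screening gain could be reported as more complications, or a real benefit could go unseen.

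**Working it through.** The Protocol gives no screening rate, undetected pool, event rate or effect size for these outcomes, so there is no figure to reproduce. What follows is an illustration, and every input is an assumption.

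**Inputs**

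- u: share with detectable but uncoded early disease, equal in both groups.
- s: share screened in a year; 50% in the comparison group, 55% or 60% in the HH group.
- q: share of unscreened disease coded anyway; 0 or 0.3.

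**First year.** Newly coded early disease = u × [s + (1 − s) × q]. In the ratio of the two groups u cancels.

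| HH screening | q = 0 | q = 0.3 |
|---|---|---|
| 55% | 0.55/0.50 = 1.10 | (0.55 + 0.45 × 0.3)/(0.50 + 0.50 × 0.3) = 0.685/0.65 = 1.05 |
| 60% | 0.60/0.50 = 1.20 | (0.60 + 0.40 × 0.3)/0.65 = 0.72/0.65 = 1.11 |

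For u = 10% and q = 0, 60% against 50% screening gives 0.10 × 0.60 = 6.0% newly coded against 0.10 × 0.50 = 5.0%, with no difference in disease.

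**Masking.** A true reduction of 1 − 1/ratio would be hidden completely. For a ratio of 1.20 this is 1 − 1/1.20 = 16.7%. For 1.054 (0.685/0.65) it is 1 − 1/1.054 = 5.1%.

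**Several years.** With a fixed undetected pool, independent yearly screening and q = 0, cumulative detection over k years is 1 − (1 − s)^k.

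| Years | 50% | 55% | 60% | Ratios to 50% |
|---|---|---|---|---|
| 3 | 1 − 0.50³ = 87.5% | 1 − 0.45³ = 90.9% | 1 − 0.40³ = 93.6% | 1.04 and 1.07 |
| 5 | 1 − 0.50⁵ = 96.9% | 1 − 0.45⁵ = 98.2% | 1 − 0.40⁵ = 99.0% | 1.01 and 1.02 |

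The excess is thus largest in the first year and shrinks as the pool empties. Newly arising disease would refill the pool and slow the decline.

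**If the six items were pooled.** The Protocol does not say that they are, so this shows only why pooling should be avoided. Assume a 1% rate of late events, a true 20% HH benefit on them, u = 10%, q = 0 and 60% against 50% screening.

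- Comparison group: 1 − (1 − 0.050)(1 − 0.010) = 5.95%.
- HH group: 1 − (1 − 0.060)(1 − 0.008) = 6.75%.
- Ratio: 6.75/5.95 = 1.13, although late events have a ratio of 0.80.

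Over twelve combinations (u of 5%, 10% or 20%, screening 5 or 10 points higher, q of 0 or 0.3) the pooled ratio runs from 0.995 to 1.17 and exceeds 1 in eleven.

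**The case against.** The strongest case on the other side has five parts.

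- **No composite is defined.** This stands. A reader might infer from the shared heading that the six items form one endpoint whose overall result moves towards harm. The list does not say so, and amputation already has its own line in Table 3. Analysed singly, the late events are not swamped by early diagnoses. The three early diagnoses remain affected either way.
- **Aim 1 has no success criterion.** This also stands. That HHs should raise these examinations is inferred from Table 2 and the Background, and only three of nine process measures are involved. For the foot exam the link runs through its sensory option only.
- **Difference-in-differences.** A reader might infer that the main analysis is difference-in-differences and fails for this reason. The Protocol names that method only for the pandemic extension (Aim 4), which contrasts 2019 with the months of 2020. For the main aims it speaks of quasi-experimental methods with matched controls. The point here rests on matching alone.
- **The size comes from assumptions.** This stands. A 20% excess is a first-year figure with no coding outside screening, and should not be quoted as the expected bias.
- **This belongs in the SAP.** Pooling, incident-case rules and sensitivity analyses may well be set out there. What the Protocol itself fixes is the outcome list, the code-based ascertainment and the double role of nephropathy. Those create the problem and should carry the caveat.

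**Conclusion.** The concern holds for three outcomes: nephropathy, neuropathy and retinopathy. As written, the plan uses code-based diagnoses as adverse outcomes while scoring the examinations that produce them as good care, and baseline matching does not separate detection from disease. End-stage renal disease, amputation and blindness are much less exposed.

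The direction of the bias is towards apparent harm or a masked benefit, provided HHs do raise screening. Its size is unknown. Under the assumed 50% against 55-60% screening it is a first-year ratio of about 1.05 to 1.20, falling to about 1.01 to 1.02 over five years with a fixed pool. A reader might infer that HHs will appear harmful in Aim 2 as a whole. The documents do not support that: apparent harm is possible rather than certain, and the intermediate, macrovascular and utilization outcomes are listed separately. This is an inexpensive improvement to interpretation, not a defect that undermines the study.

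**What to change.** Keep all six microvascular outcomes and amend the outcome section as follows.

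1. State that early diagnoses are not pooled with late events.
2. Report end-stage renal disease, amputation and blindness as the detection-robust microvascular outcomes, and rest the microvascular conclusion on them.
3. Label nephropathy, neuropathy and retinopathy as detection-dependent, and state that an increase in these alone will not be concluded to be harm. Show them beside the matching Table 2 examination rates.
4. Add a sensitivity analysis restricted to patients who were screened for the condition and free of the diagnosis before HH enrolment, or before the matched index date in the comparison group. This reduces the undetected pool at the start, though it does not stop new disease from being found sooner in the HH group. Do not restrict to patients examined in the outcome year: examination after enrolment may itself be changed by HHs, and conditioning on it can introduce selection bias.
5. Leave HbA1c, blood pressure, macrovascular outcomes and admissions in their present place in Aim 2.

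The cost is wording and one further analysis on data already held. The downside is fewer events, and so less precision, behind the microvascular conclusion, and a smaller sample in the sensitivity analysis.
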